### **Guidelines for Grading and Management of Allergic or Infusion-Related Reactions**

Allergic and/or infusion-related reactions include hypersensitivity reactions and cytokine release syndromes. These reactions are experienced by patients during or within hours of the infusion of monoclonal antibody therapy. Symptoms can include flushing, alterations in heart rate and blood pressure, dyspnea, bronchospasm, back pain, fever, urticaria, edema, nausea, and all types of rashes. Anaphylaxis is recognized as a severe, life-threatening, generalized, or systemic reaction. This is a medical emergency characterized by rapidly developing life-threatening airway and/or breathing and/or circulation problems usually associated with skin or mucosal changes.

[figure not shown]
Management of Grade 1 infusion reactions include interrupting the infusion or decreasing the rate of infusion by 50% and observing. Symptoms may also be treated as needed with medications such as diphenhydramine, hydrocortisone or acetaminophen, either alone or in combination, depending on the subject's signs and symptoms. If the infusion is interrupted or the infusion rate is decreased, it is important to note that all study drug infusions must be completed within 4 hours of SYNT001 administration.

Management of Grade 2 and higher infusion reactions should include stopping the infusion of study drug. See [Figure 1](#) and [Figure 2](#) for details on the management of Grade 2 and Grade 3 or higher infusion reactions. The severity of and management of allergic or infusion-related reactions will be graded and managed using NCI CTCAE Version 4.03 (see [Table 5](#)).

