**Figure 1: Management of Moderate (Grade 2) Infusion Reactions**

**Figure 2: Management of Severe (Grade 3 or higher) Infusion Reactions**

**Table 5: Grading and Management of Allergic or Infusion-Related Reactions**

Adverse Event	Grade				
	1	2	3	4	5
Infusion-Related Reaction	Mild transient reaction; infusion interruption not indicated; intervention not indicated	Therapy or infusion interruption indicated but responds promptly to symptomatic treatment (e.g., antihistamines, NSAIDs, narcotics, IV fluids): prophylactic medications indicated for ≤ 24 hours	Prolonged (e.g., not rapidly responsive to symptomatic medication and/or brief interruption of infusion); recurrence of symptoms following initial improvement, hospitalization indicated for clinical sequelae	Life-threatening consequences; urgent intervention required	Death
Allergic Reaction	Transient flushing or rash, drug fever < 38.0°C. Intervention not indicated	Therapy or infusion interruption indicated but responds promptly to symptomatic treatment (e.g., antihistamines, NSAIDs, narcotics, IV fluids): prophylactic medications indicated for ≤ 24 hours	Prolonged (e.g., not rapidly responsive to symptomatic medication and/or brief interruption of infusion); recurrence of symptoms following initial improvement, hospitalization indicated for clinical sequelae (e.g., renal impairment, pulmonary infiltrates)	Life-threatening consequences; urgent intervention required	Death
Anaphylaxis	-	-	Symptomatic bronchospasm, with or without urticarial; parenteral intervention indicated; allergy-related edema/angioedema; hypotension	Life-threatening consequences; urgent intervention required	Death
Cytokine release syndrome	Mild reaction; infusion interruption not indicated; intervention not indicated	Therapy or infusion interruption indicated but responds promptly to symptomatic treatment (e.g., antihistamines, NSAIDs, narcotics, IV fluids): prophylactic medications indicated for ≤ 24 hours	Prolonged (e.g., not rapidly responsive to symptomatic medication and/or brief interruption of infusion); recurrence of symptoms following initial improvement, hospitalization indicated for clinical sequelae (e.g., renal impairment, pulmonary infiltrates)	Life-threatening consequences; pressor or ventilator support indicated	Death

Abstracted from NCI CTCAE Version 4.03.

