## Grades

Grade refers to the severity of the AE. The CTCAE displays Grades 1 through 5 with unique clinical descriptions of severity for each AE based on this general guideline:

Grade 1 Mild; asymptomatic or mild symptoms; clinical or diagnostic observations only; intervention not indicated.

Grade 2 Moderate; minimal, local or noninvasive intervention indicated; limiting age-appropriate instrumental ADL\*.

Grade 3 Severe or medically significant but not immediately life-threatening; hospitalization or prolongation of hospitalization indicated; disabling; limiting self care ADL\*\*.

Grade 4 Life-threatening consequences; urgent intervention indicated.

Grade 5 Death related to AE.

A Semi-colon indicates 'or' within the description of the grade.

A single dash (-) indicates a grade is not available.

Not all Grades are appropriate for all AEs. Therefore, some AEs are listed with fewer than five options for Grade selection.

## Grade 5

Grade 5 (Death) is not appropriate for some AEs and therefore is not an option.

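### Protocol Section 9.6.1 puts as-needed medication, and interruption not limited to a precaution, under Grade 1 infusion reactions, although Table 5 makes a reaction needing either one Grade 2

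*Protocol*

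**What the plan says.** The relevant text is in the current version of Protocol Section 9.6.1, under the guidelines for grading and managing allergic or infusion-related reactions.

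- **Grade 1 management, infusion:** "Management of Grade 1 infusion reactions include interrupting the infusion or decreasing the rate of infusion by 50% and observing".
- **Grade 1 management, medication:** "Symptoms may also be treated as needed with medications such as diphenhydramine, hydrocortisone or acetaminophen". The drugs may be given alone or together, according to the subject's signs and symptoms.
- **Grade 2 and above:** "Management of Grade 2 and higher infusion reactions should include stopping the infusion of study drug".
- **Governing scale:** "The severity of and management of allergic or infusion-related reactions will be graded and managed using NCI CTCAE Version 4.03", with a reference to Table 5.

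For an infusion-related reaction, Table 5 defines Grade 1 as "Mild transient reaction; infusion interruption not indicated; intervention not indicated" and Grade 2 as "Therapy or infusion interruption indicated but responds promptly to symptomatic treatment". Appendix A carries the same CTCAE entry. Section 11.3.6 applies CTCAE 4.03 to the severity of every adverse event.

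Interruption entered the Grade 1 paragraph through the clarification letter of 11 August 2017; before that, the paragraph offered rate reduction and medication only. The same letter revised the title of Figure 1, giving consistency with the CTCAE definition of a Grade 1 reaction as a reason. In the current version, Figure 1 covers Grade 2 only.

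**The concern.** The management paragraph and the grading table sort the same reaction differently. Table 5 uses the need for therapy or interruption to separate Grade 2 from Grade 1. Section 9.6.1 lists medication given because symptoms need it as a Grade 1 measure. It also lists interruption there without saying that it means a precautionary pause.

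Two things depend on the grade. The first is the record. Adverse events are part of the primary safety measure (Section 4.2), and Section 12.5 summarises subjects by preferred term at their most severe grade. Grading is done at about 10 sites (Section 4.1), so the two readings could be applied unevenly. The second is the infusion itself. A Grade 1 reaction may be medicated while the drug runs on at half rate, whereas Grade 2 calls for the infusion to be stopped.

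**Working it through.** The point is a comparison of texts, and the protocol gives no figure to reproduce. Five situations cover what Section 9.6.1 allows at Grade 1. Each is assumed to be mild and to resolve promptly.

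| Situation | Section 9.6.1 | Table 5 | Agreement |
|---|---|---|---|
| Observation only | Grade 1 | Grade 1 | yes |
| Rate halved, nothing else | Grade 1 | rate reduction not named | no conflict |
| Paused purely as a precaution | Grade 1 | Grade 1, as interruption was not indicated | yes |
| Paused because the reaction required it | can be read as Grade 1 | Grade 2 | **no** |
| Medicated because symptoms required it | Grade 1 | Grade 2 | **no** |

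The last row is the clearest conflict. Table 5 describes a Grade 2 reaction as one that "responds promptly to symptomatic treatment (e.g., antihistamines, NSAIDs, narcotics, IV fluids"; diphenhydramine, the first drug named for Grade 1 in Section 9.6.1, is an antihistamine. The general CTCAE guideline in Appendix A points the same way: "Grade 1 Mild; asymptomatic or mild symptoms; clinical or diagnostic observations only; intervention not indicated". Medication given as needed, according to signs and symptoms, is hard to tell apart from therapy that is indicated.

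Other rows of Table 5 give the same boundary. Cytokine release syndrome has the same Grade 1 and Grade 2 criteria on interruption and intervention. Allergic reaction excludes indicated intervention from Grade 1 and puts therapy or interruption at Grade 2.

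**What one subject weighs.** If one subject's worst grade for the term is recorded as 1 instead of 2, the Grade 1/2 split moves by:

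- one cohort of 8: 1/8 = 12.5 percentage points;
- two cohorts, 16 subjects: 1/16 = 6.25 points;
- three cohorts, 24 subjects: 1/24 = 4.2 points.

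These figures are the weight of one subject and would hold for any misgraded event. They do not estimate how many subjects are affected. The instruction applies to 8 × 5 = 40 planned infusions per cohort, not counting replacements.

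**What does not move.** A subject with a reaction is counted as having one at either grade. The dose-escalation rule (Section 8.4.1) turns on related, clinically significant Grade 3 events in 2 or more subjects. The study stopping rule (Section 8.4.2) turns on a related Grade 4 event. The individual stopping rule (Section 8.4.3) uses relatedness, seriousness and judgement, not grade. A shift between Grades 1 and 2 reaches none of them.

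**The case against.** The strongest reply is that Section 9.6.1 itself names CTCAE 4.03 and Table 5 as the rule for both grading and management, and Section 11.3.6 repeats the grading rule. Table 5 grades by what is indicated, not by what is given. On that reading, the Grade 1 paragraph only lists options for a reaction already graded 1, and a careful investigator will still grade correctly. Allowing a pause for mild reactions was also the sponsor's deliberate choice, explained in the August 2017 letter.

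Much of this stands. A reader might infer that Section 9.6.1 leaves its Grade 1 measures without any link to CTCAE; it does not, because the governing sentence is there. A reader might also infer that every pause or slowing at Grade 1 contradicts Table 5. It does not: rate reduction is absent from Table 5, and an optional or precautionary pause does not make interruption indicated.

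What the reply does not remove is the medication sentence. Naming Table 5 as governing makes that sentence conflict with the section's own rule, since drugs given because symptoms need them are therapy indicated. Nor does the paragraph say that interruption is meant only as a precaution.

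It can also be said that handling hardly differs between the grades. Figure 1 is not visible in the text at hand, so how long a Grade 2 infusion stays stopped, and whether it resumes, cannot be judged. The visible instructions do differ on one point: Grade 1 allows continuing at half rate with medication, and Grade 2 says to stop.

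**Conclusion.** The inconsistency is real, sits in the current text and is narrow. A promptly resolving reaction that needed medication or interruption can be called Grade 1 under the management paragraph of Section 9.6.1, while Table 5 makes it Grade 2. The consequence is limited to the Grade 1/2 split in the treatment-emergent adverse event tables and to whether the stop instruction is applied.

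A reader might infer that dose escalation or study stopping is at risk, or that reactions would go uncounted. The documents support neither. Nor can the size of the problem be taken from Phase 1a. The letter reports no infusion reactions there, but that was a single-dose study in healthy volunteers and says nothing about how many mild, treated reactions would be misgraded among patients given five doses. The number affected is unknown.

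The conclusion assumes that some sites would read the Grade 1 paragraph as describing what a Grade 1 reaction looks like. Affected cases could be traced afterwards, because treatment of each event is recorded (Section 11.3.6) and action taken is listed (Section 12.5). The wording should be corrected because grade is part of a primary safety measure and the correction is cheap; the inconsistency does not threaten the trial.

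**What to change.** Replace the Grade 1 paragraph of Section 9.6.1 with wording such as:

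*Grade 1 (no interruption or therapy indicated): observe; the infusion may be slowed by 50% or paused as a precaution. If symptoms require medication or interruption, the reaction is Grade 2 by Table 5 and is recorded and managed as Grade 2.*

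The existing time limit on completing a slowed or paused infusion stays.

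The cost is a short amendment and a real shift in practice: some mild treated reactions now called Grade 1 would be reported as Grade 2 and would have the infusion stopped under the Grade 2 instruction. Investigators would still have to judge whether a pause was precautionary or required, but the paragraph would then draw that line where Table 5 does.

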**Figure 1: Management of Moderate (Grade 2) Infusion Reactions**

**Figure 2: Management of Severe (Grade 3 or higher) Infusion Reactions**

**Table 5: Grading and Management of Allergic or Infusion-Related Reactions**

Adverse Event	Grade				
	1	2	3	4	5
Infusion-Related Reaction	Mild transient reaction; infusion interruption not indicated; intervention not indicated	Therapy or infusion interruption indicated but responds promptly to symptomatic treatment (e.g., antihistamines, NSAIDs, narcotics, IV fluids): prophylactic medications indicated for ≤ 24 hours	Prolonged (e.g., not rapidly responsive to symptomatic medication and/or brief interruption of infusion); recurrence of symptoms following initial improvement, hospitalization indicated for clinical sequelae	Life-threatening consequences; urgent intervention required	Death
Allergic Reaction	Transient flushing or rash, drug fever < 38.0°C. Intervention not indicated	Therapy or infusion interruption indicated but responds promptly to symptomatic treatment (e.g., antihistamines, NSAIDs, narcotics, IV fluids): prophylactic medications indicated for ≤ 24 hours	Prolonged (e.g., not rapidly responsive to symptomatic medication and/or brief interruption of infusion); recurrence of symptoms following initial improvement, hospitalization indicated for clinical sequelae (e.g., renal impairment, pulmonary infiltrates)	Life-threatening consequences; urgent intervention required	Death
Anaphylaxis	-	-	Symptomatic bronchospasm, with or without urticarial; parenteral intervention indicated; allergy-related edema/angioedema; hypotension	Life-threatening consequences; urgent intervention required	Death
Cytokine release syndrome	Mild reaction; infusion interruption not indicated; intervention not indicated	Therapy or infusion interruption indicated but responds promptly to symptomatic treatment (e.g., antihistamines, NSAIDs, narcotics, IV fluids): prophylactic medications indicated for ≤ 24 hours	Prolonged (e.g., not rapidly responsive to symptomatic medication and/or brief interruption of infusion); recurrence of symptoms following initial improvement, hospitalization indicated for clinical sequelae (e.g., renal impairment, pulmonary infiltrates)	Life-threatening consequences; pressor or ventilator support indicated	Death

Abstracted from NCI CTCAE Version 4.03.

### 9.6.2 Potential Immune Effects

An antibody blocking FcRn is anticipated to have several effects. These include acceleration of catabolism of IgG, but not other immunoglobulin isotypes such as IgA and IgM, leading to dose-dependent decreases in circulating IgG levels by up to an estimated 50% from the baseline levels after a single dose and further decreases after multiple doses up to a 70% to 80% reduction. Based on studies in humans, it is expected that with a single dose, the nadir of this effect will occur approximately 5 days after dosing. The time course of recovery of IgG following dosing in the Phase 1a study suggests that a return to within 30% of baseline levels observed at pretreatment occurs within 4 weeks after a single dose and within 4 weeks after multiple doses as shown in NHPs.

Given the normal adult range of IgG of 500 to 1600 mg/dL ([Agarwal and Cunningham-Rundles, 2007](#); [Furst, 2009](#); [Gonzalez-Quintela et al., 2008](#); [Jolliff et al., 1982](#); [Keystone et al., 2007](#); [McMillan et al., 1997](#); [van Vollenhoven et al., 2013](#)), with a mean of 1150 mg/dL, a 50% decrease in the mean would be to 575 mg/dL and a 50% decrease from the low end of the normal range used for the inclusion criteria of 600 mg/dL would be to 300 mg/dL. An 80% decrease from baseline after multiple doses would result in IgG levels of 230 mg/dL and 120 mg/dL, respectively. While these levels are in the range found in patients with primary humoral immunodeficiency ([Ameratunga et al., 2013](#)), the levels will be transient. Further, as reported for other therapies used for pemphigus, the temporary (ie, less than 4 months) depletion of IgG (up to 95% reduction of total IgG as seen with immunoadsorption) does not appear to impart an increased risk of infection ([Eming and Hertl, 2006](#); [Furst, 2009](#); [Keystone et al., 2007](#); [Schmaldienst et al., 2001](#); [van Vollenhoven et al., 2013](#)). Study subjects will be monitored clinically for any infection. Further, commercial IVIG can be given to reverse the low IgG levels in case of a bacterial infection occurring while their IgG levels are decreased.

An antibody blocking FcRn is expected to also down modulate innate and adaptive immunity and the catabolism of IgG-containing immune complexes (IC). Specifically, it is expected that anti-FcRn will promote the clearance of IgG-containing ICs and the effects of these IC on stimulating innate immune cell production of inflammatory cytokines (e.g., IL-12, interferon- $\gamma$ , and tumor necrosis factor [TNF]) and inhibit the processing and presentation of antigens contained within IC and thus the antigen-specific activation of CD4+ and CD8+ T-cells. Therefore, subjects with pre-existing conditions that are dependent upon IgG antibodies, such as chronic infections (e.g., HIV, HBV or HCV), will be excluded from this study, as will subjects with active infection in general.

SYNT001 administration could decrease the level of protective antibodies from prior vaccinations. Protective antibody levels for tetanus and varicella-zoster virus (chickenpox) are to be tested in accordance with [Section 6.7.3](#).

## 10 CONCOMITANT MEDICATION AND TREATMENT

All treatments a subject receives within 14 days prior to enrollment through the end of the study will be documented. Concomitant medication and treatment for co-existing conditions, including those for pemphigus, are permitted if not excluded below. Topical antibiotics are permitted to treat active infections that occur on study. Topical or systemic treatments for oral candidiasis are permitted. Topical lidocaine for transient pain relief is acceptable as needed. Significant increases in anti-pemphigus medications will result in subjects being discontinued from the study. Concomitant treatment that is medically indicated for any AEs the subject experiences during the study are permitted. Premedication is discouraged as prophylaxis against AEs or infusion reactions unless medically indicated from either past medical history, prior infusion reactions or AEs resulting from SYNT001 infusions.

Use of the following treatments will not be permitted during the study unless otherwise specified:

- Rituximab or other anti-CD20 antibody
- Monoclonal antibodies other than study drug
- Any immunosuppressive drugs apart from corticosteroids, azathioprine, mycophenolate mofetil, or cyclosporine.
- Topical steroids
- Any dietary herbal supplements
- Any investigational drug or device
- Any vaccinations through Day 56. Following Day 56, subjects may be vaccinated at the discretion of the Investigator.

If over a period of at least two weeks on study drug, a subject on corticosteroids shows the absence of new lesions and significant healing of lesions that existed at study baseline, a slow corticosteroid taper may be started as per the following suggested schedule

- If on > 30 mg of prednisone per day, decrease by 10 mg every two weeks until a dose of 30 mg per day then decrease by 5 mg every two weeks
- If on < 30 mg of prednisone per day, decrease by 5 mg every two weeks

In cases in which concomitant medications are used, details to be recorded include the following: medication name, start date and time, stop date and time, dose, route, frequency, and reason for use. The concomitant medication names are to be coded using the World Health Organization (WHO) Drug Dictionary (WHO-DD March 2013, Type B2 or later) and classified by anatomical therapeutic chemical (ATC) categories.

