### **5.3 Exclusion Criteria**

A subject who meets any of the following criteria is ineligible for the study:

1. Unable or unwilling to comply with the protocol;
2. Active non-hematologic malignancy or history of non-hematologic malignancy in the 3 years prior to screening (exclusive of non-melanoma skin cancer and cervical cancer in situ);
3. Positive for HIV or hepatitis C antibody;
4. Positive for hepatitis B surface antigen;
5. Active infection or history of recurrent infections;
6. IVIG treatment within 60 days of screening;
7. Received any cytotoxic (other than azathioprine) or mAb therapy in the 3 months prior to screening;

8. Any exposure to an investigational drug or device within 30 days prior to screening;
9. Plasmapheresis or immunoadsorption within 60 days of screening
10. Cellular therapy, including CAR-T, at any time prior to screening
11. Use of any immunosuppressive drugs apart from corticosteroids, azathioprine, mycophenolate mofetil, or cyclosporine within 3 months of screening;
12. Serum total IgG < 600 mg/dL;
13. Subject has any current medical condition that, in the opinion of the Investigator, may compromise their safety or compliance, preclude successful conduct of the study, or interfere with interpretation of the results (e.g., a significant pre-existing illness or other major comorbidity that the Investigator considers may confound the interpretation of the study results);
14. Any vaccination within 2 weeks of screening

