#### 12.3.1 Study Populations

Three populations will be employed in the analysis of study data:

- The **intent-to-treat (ITT)** population will consist of all subjects who have received at least one dose of study drug. All safety analyses will be performed on the ITT population.
- The **PK** population will consist of all subjects who receive at least one dose of study drug and have sufficient post-dose blood samples to obtain PK parameters.
- The **PD** population will consist of all subjects who receive at least one dose of study drug and have post-dose PD data available.

Primary safety analyses will be performed on the ITT population. Demographics, subject disposition, and screening and baseline characteristics will be summarized for the ITT, PK, and PD populations, where appropriate.

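### IVIG, plasmapheresis and immunoadsorption are washed out before entry but missing from Section 10's prohibited list, and the limit on pemphigus rescue is stated two ways, so some IgG and anti-Dsg values could reflect rescue rather than SYNT001

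*Protocol*

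**What the plan says.** **At entry.** Protocol Section 5.3 excludes subjects with "IVIG treatment within 60 days of screening" (Exclusion 6) and "Plasmapheresis or immunoadsorption within 60 days of screening" (Exclusion 9).

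**On study.** Section 10, repeated in the synopsis under prohibited concomitant treatments, states: "Concomitant medication and treatment for co-existing conditions, including those for pemphigus, are permitted if not excluded below". The list that follows covers anti-CD20 and other monoclonal antibodies, topical steroids, herbal supplements, investigational products, vaccinations through Day 56, and "Any immunosuppressive drugs apart from corticosteroids, azathioprine, mycophenolate mofetil, or cyclosporine". It names none of the three treatments. Section 10 adds: "Concomitant treatment that is medically indicated for any AEs the subject experiences during the study are permitted".

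**IVIG for infection.** Section 9.6.2 says that "commercial IVIG can be given to reverse the low IgG levels in case of a bacterial infection occurring while their IgG levels are decreased".

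**The limit on rescue.** Section 10 says: "Significant increases in anti-pemphigus medications will result in subjects being discontinued from the study". For the same trigger, Section 8.4.3 stops further study drug only, at the Investigator's discretion in consultation with the Medical Monitor.

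**What is measured.** Section 4.2 makes total IgG, IgG1-4 and anti-Dsg 1 and 3 secondary outcomes. Table 4 samples them to Day 112; the last dose is on Day 28. Sections 5.1 and 8.3 keep subjects who miss doses in follow-up through all scheduled visits. The PD population in Section 12.3.1 is every dosed subject who "have post-dose PD data available".

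**The concern.** The three treatments act directly on the quantities that the trial uses to show drug activity. IVIG adds IgG and could hide how deep or how long the suppression was. Plasmapheresis and immunoadsorption remove IgG, autoantibody included, and could look like drug effect on total IgG, the subclasses and anti-Dsg. Donor IgG could also affect the tetanus and VZV comparisons with baseline in Section 6.7.3.

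Their use is foreseeable from the protocol itself. Section 2 names IVIG and plasmapheresis among current treatments for autoimmune disorders, and Section 9.6.2 counts immunoadsorption among therapies used for pemphigus. A site that follows Section 10 literally would find nothing that bars them. What happens to the subject afterwards depends on which section the site reads.

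**Working it through.** **1. Does any listed item cover the three treatments?** The nearest is the item on immunosuppressive drugs. Section 5.3 treats that as a separate category: immunosuppressive drugs are Exclusion 11, IVIG is Exclusion 6, and plasmapheresis and immunoadsorption are Exclusion 9. On the protocol's own classification the item does not reach them.

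**2. Does the clause on significant increases close the gap?** Not reliably:
- It speaks of medications and doses, not procedures, and does not define a significant increase.
- It does not reach IVIG given for an infection.
- Section 10 takes the subject off the study; Section 8.4.3 takes the subject off study drug.
- After Day 28 there is no dosing left to stop, while sampling runs for a further 112 − 28 = 84 days.
- A subject who leaves the study is still to have the Early Termination visit, which includes IgG and anti-Dsg draws.
- Section 11.2 counts exacerbation of a pre-existing condition as an AE, so the AE-treatment sentence is a second route.

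**3. The protocol's IgG figures (Section 9.6.2) reproduce.** Level = baseline × (1 − reduction):
- 1150 × 0.5 = 575 and 600 × 0.5 = 300 mg/dL
- 1150 × 0.2 = 230 and 600 × 0.2 = 120 mg/dL

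**4. Illustration, one affected subject in a cohort of 8.** Apparent mean reduction = (7 × true + value in the affected subject) / 8. That one subject is affected is an assumption.

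*Immunoadsorption*, at the 95% reduction cited in Section 9.6.2:
- true 50%: (350 + 95)/8 = 55.6%
- true 70%: (490 + 95)/8 = 73.1%
- true 80%: (560 + 95)/8 = 81.9%

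*IVIG*, true reduction 80%, starting from 230 mg/dL. The protocol gives no IVIG dose. Assumed: 70 kg, 0.2 to 0.4 g/kg, distribution volume 3 to 6 L (30 to 60 dL).
- Low end: 0.2 × 70,000 mg / 60 dL = 233 mg/dL. Then 230 + 233 = 463 mg/dL, which is 40% of 1150, a reduction of about 60%. Cohort mean: (560 + 60)/8 = 77.5%.
- High end: 0.4 × 70,000 / 30 = 933 mg/dL. Then 230 + 933 = 1163 mg/dL, about baseline. Cohort mean: (560 + 0)/8 = 70.0%.

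**5. Chance that a cohort of 8 contains at least one such subject.** 1 − (1 − p)^8, with p assumed because the protocol gives none: 34% for p = 5%, 57% for p = 10%, 83% for p = 20%.

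**The case against.** Much of the case on the other side stands.

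- *Different rules at entry and on study are normal.* A washout protects the baseline. The difference alone is not an error, and the entry bar is only a 60-day window.
- *IVIG for infection is consistent.* A reader might infer that Section 9.6.2 contradicts Section 10, or that low IgG alone is a ground for IVIG. Neither is supported. Section 9.6.2 ties IVIG to a bacterial infection while IgG is decreased, and Section 10 permits treatment indicated for AEs.
- *Handling of values after rescue belongs to the SAP.* Section 12.3 defers detailed methods to it and it is not at hand. The absence of an analysis rule here is not a fault, and it cannot be said that such values will enter the summaries unadjusted.
- *The size is limited.* The 70% figure needs the highest assumed dose and the smallest volume, and ignores that FcRn blockade may speed the loss of infused IgG. A minimum already recorded cannot be raised by later IVIG. Medians, ranges and listings are planned, and treatments are recorded with dates and reasons.
- *Escalation is not driven mechanically by a cohort mean.* The committee weighs total IgG with AEs and SAEs, and Section 12.8 plans no statistical analyses to aid its decisions.
- *Starting plasmapheresis or immunoadsorption could be read as a significant increase in anti-pemphigus treatment.* This is plausible, but the clause does not say so, and its two versions lead to different follow-up.

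What remains is that Section 10 permits by default, omits treatments acting on the secondary endpoints, and has one limit with two incompatible consequences. An SAP cannot settle what sites may give or whether a subject stays on study.

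**Conclusion.** The point holds as a gap in the on-study list and an inconsistency in the limit on rescue, of minor to moderate weight. Values taken after IVIG, plasmapheresis or immunoadsorption could mask or mimic the SYNT001 effect on total IgG, IgG1-4 and anti-Dsg. With one affected subject in 8, the shift in mean IgG reduction is about 2 to 6 percentage points upward after immunoadsorption, for true reductions of 80% down to 50%. After IVIG, with a true reduction of 80%, it is 2.5 to 10 points downward, with 10 the worst case. The upward figures rest on the protocol's 95%; the downward ones on assumed weight, dose and volume.

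A reader might infer that the trial's IgG results will be determined by rescue. The documents do not support that: they give no rate of use, and one subject distorts individual values and moves a mean rather than fixing the whole result.

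**What to change.** Reconcile Sections 5.3, 8.4.3, 9.6.2 and 10, and the matching synopsis entries, so that the on-study status of the three treatments and the consequence of receiving them (off study drug or off study) are stated once and consistently. This review takes no view on which treatments should be allowed.

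Where any of them is given, flag all later values of total IgG, IgG subclasses, anti-Dsg and tetanus/VZV antibodies, and present the cohort PD summaries with and without those values. If the SAP already does this, only the reconciliation is needed.

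The cost is a short text change and slightly more analysis; dates of treatment are already collected. The summaries without post-rescue values have their own weakness. They may drop the more deeply suppressed subjects, those with an infection while IgG was low, and so make recovery look faster. That is why both versions should be shown.
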